#### **Enrollment Sample Size**

The study size will be 250 enrolled subjects. The goal is 100 with metastatic lesions involving only the vertebral body, 100 with metastatic lesions outside the vertebral body, and 50 with benign bone tumors. The increased sample size will allow for richer safety reporting and long-term follow-up.

### 7. Statistical Methods

### 7.1 Study Subjects

### 7.1.1 Disposition of Subjects

Subject disposition will be summarized by study visit in a flow diagram. Discontinuations will be summarized by visit, and discontinuation reasons will be provided.

Revision 1.0

Page 8 of 15

### 7.1.2 Clinical Investigation Plan (CIP) Deviations

CIP deviations occurring during the study will be summarized by deviation type.

### 7.1.3 Analysis Sets

#### **Analysis Sets**

There are 3 analysis sets:

**Enrolled**: all enrolled subjects. The demographics of this set, and specifically the subjects in this set but not in the Treated Analysis set, will only briefly be characterized. Otherwise, the efficacy and safety analyses will be on the following two analysis sets.

The analysis sets to be included in the efficacy analyses (primary objective, secondary objective, and additional measures) are described below.

**Treated Analysis Set**: all subjects who are successfully treated with the OsteoCool™ RF Ablation system.

**Completers Analysis Set**: the subset of Treated Analysis Set subjects who provided endpoint data at the 3-Month Visit. The Completers Analysis Set will be a subset of the Treated Analysis Set. The Completers Analysis Set will be the analysis population for the primary objective hypothesis testing.

The safety analyses will utilize the Treated Analysis Set.

#### **Objective Cohorts**

There will be two objective cohorts, which will be used to separate the subjects to be analyzed in the primary objective versus the secondary objective. At the time of treatment with the OsteoCool™ RF Ablation system, subjects will get assigned to one of the two cohorts depending on the lesion type(s) treated. The two cohorts encompass the entire set of Treated Analysis Set subjects and are mutually exclusive. Each objective cohort will have a Treated Analysis Set and a Completers Analysis Set.

There will be a small number of subjects that are enrolled, but do not undergo the RFA procedure. They will not be assigned to an objective cohort.

**Primary Objective Cohort**: subjects with metastatic lesions involving the vertebral body only **Secondary Objective Cohort**: subjects with metastatic lesions outside the vertebral body and/or benign bone tumors. This includes subjects with a combination of lesions involving the vertebral body and outside the vertebral body. This cohort may get divided further depending on treatment site (for example: non-vertebral bone, benign bone tumors, combinations).

[figure not shown]
### 7.2 General Methodology

Data analysis will be performed by Medtronic-employed statisticians or designees. A validated statistical software package (e.g., SAS version 9.4 or higher) will be used to analyze the study results.

The analysis methods are provided for each objective in Section Error! Reference source not found.

Revision 1.0

Page 9 of 15

### 7.3 Center Pooling

Due to the relatively small number of subjects expected at each center, there is no plan to use statistical methods to test for a difference among centers. Primary objective results will be summarized by center to verify there is not a site that unduly influences the results, and will be included in reports if there are concerns about the center effect.

There is no plan to exclude any centers from the analysis.

For the overall study size of 250, each center can contribute no more than 50 subjects (from both subject cohorts combined) without prior Medtronic approval.

### 7.4 Handling of Missing, Unused, and Spurious Data and Dropouts

The primary and secondary objective endpoint assessments are planned to be collected at the 3-Month follow-up visit.

Imputation of values for missing data for primary and secondary efficacy analyses will be performed as follows.

Completers Analysis Set: The Completers Analysis Set will be analyzed without imputations for missing data. (By definition, the endpoint data was provided.) Based on published data in this patient population (Bagla, 2016) it is assumed that the primary reasons for missing endpoint data will be death or inability to contact subjects due to deteriorating health and not related to pain score level. Thus, inclusion in the Completers Analysis Set is assumed to not be confounded with endpoint pain score level.

Sensitivity Analysis: The Treated Analysis Set is expected to have missing endpoint data. The frequency, timing, and reasons for missing data will be reported and analyzed to assess potential for bias. Sensitivity analyses of the primary objective, detailed in the primary objective Analysis Methods section below, will include analyzing the Treated Analysis Set using multiple imputation and single imputation.

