#### **Missing Endpoint Data**

Study centers will be instructed to make every effort to keep subjects actively attending study visits. The primary and secondary objective assessments are planned to be collected at the 3-Month follow-up

#MDT16075 Version 4.0 Page 56 of 81

visit. If subjects miss their scheduled 3-Month follow-up visit, the investigator will attempt to collect the data within the visit window or before study discontinuation. Phone calls may also be utilized to obtain data for the primary endpoint.

Completers population: The Completers population will be analyzed without imputations for missing data. (By definition, the endpoint data was provided.) It is assumed that the primary reasons for missing endpoint data will be death or inability to contact subjects due to deteriorating health (Bagla) and not related to pain score level. Thus, inclusion in the Completers population is assumed to not be confounded with endpoint pain score level.

Sensitivity Analysis: The Treated population is expected to have missing endpoint data. The frequency, timing, and reasons for missing data will be reported and analyzed to assess potential for bias. Sensitivity analyses of the primary objective, detailed in the primary objective analysis methods section below, will include analyzing the Treated population using multiple imputation and single imputation. The results of these analyses may suggest other specific sensitivity analyses or imputation strategies.

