#### 13.3.6. Analysis Methods

A two-sided t-test with alpha=0.05 will be used to test the null hypothesis of no change in worst-pain score between baseline and 3 months.

If the distribution of the change scores does not meet the assumption of normality, the non-parametric Wilcoxon signed-rank test will be used to test for significant change with alpha=0.05, two-sided.

The primary objective hypothesis will be tested after the sample size requirements for it have been met. If additional subjects are enrolled later and also treated for metastatic lesions involving only the vertebral body, those additional subjects will be combined with the first group and summarized together.

The main analysis for the primary objective hypothesis testing will be on the Completers population.

In order to include all the treated subjects in the analysis, a sensitivity analysis will be performed on the Treated population. The endpoint data will first undergo multiple imputations (MI). Rather than filling in a single value for each missing value, MI replaces each missing value with a set of "plausible" values that represent the uncertainty about the correct value to impute. These multiple imputed datasets are then analyzed using standard statistical procedures and then combined into one analysis result with an appropriately increased variance. Included in the MI analysis will be the endpoint variable at 3 months and the endpoint variable at baseline, 3 days, 1 week, 1 month, and unscheduled visits (if collected), as well as baseline covariates. The method to be used is the Markov chain Monte Carlo (MCMC) method of SAS (version 9.4 or higher). This is an iterative method that can be used when the pattern of missing data is arbitrary (monotone or non-monotone). The default number of iterations will be used (n=5) and, if needed, will be increased until the Markov chain converges.

A single imputation method will also be performed, substituting the Treated population's endpoint variable at the last available follow-up (Bagla) for the missing endpoint variable.

Sensitivity analyses will be performed, separating the evaluation by whether or not the subjects received vertebral augmentation procedures and/or post RFA radiation therapy.

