#### **Analysis Methods**

Revision 1.0

Page 11 of 15

The main analysis for the primary objective hypothesis testing will be on the Primary Objective Cohort using the Completers Analysis Set.

A two-sided t-test with alpha=0.05 will be used to test the null hypothesis of no change in worst-pain score between baseline and 3 months. If the p-value is <0.05, the primary objective will be demonstrated, and statistical significance will be declared.

If the distribution of the change scores does not meet the assumption of normality, by calculating the Shapiro-Wilk W statistic probability, the non-parametric Wilcoxon signed-rank test will be used to test for significant change with alpha=0.05, two-sided. P-values less than 0.05 for the Shapiro-Wilk statistic will indicate non-normality.

In order to include all the treated subjects in the analysis, a sensitivity analysis will be performed on the Treated Analysis Set. The endpoint data will first undergo multiple imputations (MI). Rather than filling in a single value for each missing value, MI replaces each missing value with a set of "plausible" values that represent the uncertainty about the correct value to impute. These multiple imputed datasets are then analyzed using standard statistical procedures and then combined into one analysis result with an appropriately increased variance. The model variables in the MI analysis may include the following when deemed appropriate: the endpoint variable at 3 months and the endpoint variable at baseline, 3 days, 1 week, and 1 month, baseline covariates of subject age, Karnofsky score, and time from primary cancer diagnosis to baseline. The method to be used is the Markov chain Monte Carlo (MCMC) method of SAS (version 9.4 or higher). This is an iterative method that can be used when the pattern of missing data is arbitrary (monotone or non-monotone). The default number of iterations will be used (n=25) and, if needed, will be increased until the Markov chain converges. The seed will be "16075".

To allow comparison to Bagla (2016) results, a single imputation method, Last Observation Carried Forward, will also be performed, substituting the Treated Analysis Set's endpoint variable at the last available follow-up for the missing endpoint variable.

The analyses above are for the Primary Objective Report. For the Final Study Report, descriptive statistics, as well as confidence intervals, of the change in pain will be reported.

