In the Primary Objective Report, the sensitivity analyses will include Treated Analysis Set subjects that have procedure dates before the last subject's procedure date in the Completers Analysis Set. In other words, subjects recently treated, but not expected to have been followed for the whole 3 months at the time of the snapshot, will not be in the sensitivity analyses.

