### 7.11 Changes to Planned Analysis

There are no changes to the planned analysis.

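### The primary test uses completers only; neither planned sensitivity analysis lets missing subjects do worse than the imputation model or their last score implies, and the SAP makes the pain scores in that model optional

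*Combined protocol and SAP*

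**What the plan says.** **Primary analysis.** CIP 13.3.6 and SAP 7.9.1 run a two-sided test of zero mean change at alpha 0.05 on the completers, without imputation. SAP 7.4 expects scores to be missing through death or failing health rather than pain level, and concludes that "inclusion in the Completers Analysis Set is assumed to not be confounded with endpoint pain score level". CIP 13.1.4 says the same.

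**Sensitivity analyses for missing scores.** There are two, both on the treated set: MCMC multiple imputation and LOCF. CIP 13.1.4 adds "The results of these analyses may suggest other specific sensitivity analyses or imputation strategies", but names none, and the SAP does not repeat the sentence. SAP 7.9.1 limits the set by date: "the sensitivity analyses will include Treated Analysis Set subjects that have procedure dates before the last" completer's procedure.

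**Imputation model.** CIP 13.3.6 states as a commitment that the model will hold the 3-month score and the "endpoint variable at baseline, 3 days, 1 week, 1 month, and unscheduled visits (if collected), as well as baseline covariates". SAP 7.9.1 says instead "The model variables in the MI analysis may include the following when deemed appropriate", and then lists the baseline, 3-day, 1-week, 1-month and 3-month scores with age, Karnofsky score and time from diagnosis. SAP 7.11 reads "There are no changes to the planned analysis".

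**Reasons for leaving.** CIP 9.11 asks for notes on why a subject withdrew. Its examples include discomfort and lack of efficacy beside loss to follow-up and death.

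**The concern.** The study has one arm and reports a mean change. Any difference in 3-month pain between completers and missing subjects therefore passes straight into the treated-population estimate, in proportion to the fraction missing. The assumption that completion is unrelated to pain sits badly with the CIP's own example reasons for withdrawal, and failing health may plausibly go with worse pain.

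The sensitivity analyses replace that assumption with two others. MI assumes that missing scores follow the model given what was observed; LOCF assumes that the last score persists. Both can agree with the completers' result and still be wrong in the same direction if pain rose after the last recorded score.

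MI is the one planned analysis that can correct dropout explained by earlier pain, but only if the earlier pain scores are in the model. The SAP leaves that to later judgement.

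**Working it through.** **Step 1. Reproduce the plan's figures (CIP 13.3.5, SAP 6).** Inputs: difference 2, SD 3.5, two-sided alpha 0.05, power 0.90, loss 32%.
- Noncentral t power is 0.8986 at n = 34 and 0.9072 at n = 35, so 35 completers. This matches.
- 35/0.68 = 51.5, so 52 treated. This matches.
- Planned missing: 52 - 35 = 17, and 17/52 = 32.7%.

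**Step 2. Shift in the estimate.** Let completers have mean -2.0, and let g be the net gap by which missing subjects are worse. The treated mean is -2.0 + (17/52)g. The documents give no value for g, so a range is shown. Two simple standard errors are used:
- (a) *Fixed:* SE = 3.5/√35 = 0.592, 34 df.
- (b) *Missing scores treated as observed:* SD² = [50 × 3.5² + (35 × 17/52)g²]/51 and SE = SD/√52, 51 df.

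| Net gap g | Missing mean | Treated mean | p, (a) | p, (b) |
|---|---|---|---|---|
| 1 | -1 | -1.67 | 0.008 | 0.001 |
| 2 | 0 | -1.35 | 0.029 | 0.009 |
| 3 | +1 | -1.02 | 0.094 | 0.055 |
| 4 | +2 | -0.69 | 0.25 | 0.21 |

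For comparison, the completers alone give p = 0.0018 (95% CI -3.20 to -0.80).

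**Step 3. Tipping point.**
- Under (a), significance is lost when the treated mean reaches -(2.032 × 0.592) = -1.202. So g = (2 - 1.202) × 52/17 = 2.44, a missing mean of +0.44.
- Under (b), g = 2.94, a missing mean of +0.94.
- Delta-adjusted MI with Rubin's rules and no cap, at assumed 1-month to 3-month correlations of 0.3, 0.5 and 0.7, tips at 2.30, 2.37 and 2.57. This is close to (a).

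**Step 4. Net gap against nominal delta.** Worst pain cannot exceed 10. With imputed scores capped at 10, and an assumed baseline mean of 6 to 8 (SD 1.6) and SD of change 3.5, a nominal delta of 4 is a net shift of only about 2.8 to 3.35. The gaps in steps 2 and 3 are net, so the nominal tipping delta under the cap is larger than they suggest.

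**Step 5. A larger effect.** The cited prospective ablation series fell from 5.9 to 2.1 (CIP 4.4), a drop of 3.8. If completers improve by 3.8 and missing subjects do not change, the treated mean is -3.8 × 35/52 = -2.56 (95% CI under (a) -3.76 to -1.36). Significance is lost only if missing subjects worsen by about 3.6 (b) to 4.1 (a).

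**Step 6. What the optional pain scores are worth.** Assumptions: multivariate normal changes at 3 days, 1 week, 1 month and 3 months, SD 3.5, step correlation 0.3, 0.5 or 0.7, logistic dropout with slope 1 per SD, and 32.7% missing. Overstatement of benefit, in points:

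| Dropout depends on | Analysis | 0.3 | 0.5 | 0.7 |
|---|---|---|---|---|
| 1-month score | Completers | 0.29 | 0.49 | 0.67 |
| 1-month score | MI without the 1-month score | 0.26 | 0.38 | 0.36 |
| 1-month score | MI with the 1-month score | about 0 | about 0 | about 0 |
| Unseen 3-month score | Full MI model | 0.88 | 0.75 | 0.52 |

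The third row assumes that every dropout has a 1-month score. If half lack it, 0.14 to 0.19 points remain. The last row shows what no choice of variables removes.

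**The case against.** The plan does a good deal already.
- CIP 13.1.4 has sites seek the endpoint within the window or before discontinuation, by phone if needed. The 3-month window is ±30 days.
- Under CIP 9.11, a subject withdrawn between visits gets an unscheduled-visit form, except on death or loss to follow-up. Table 9-1 includes the pain questionnaire at such visits. LOCF as worded can therefore carry worsening recorded at exit.
- Discontinuations are reported by visit with reasons (SAP 7.1.1). The frequency, timing and reasons for missing data are analysed (SAP 7.4), and deaths are shown with the events committee's determination (SAP 7.10).

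All of this stands. It reduces missing data and can flag bias. It does not size bias for subjects whose pain rose after their last score, and no estimate with and without early deaths is planned.

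Three stronger readings are tempting, and the documents do not support them.
- *A reader might infer that the SAP conceals deaths.* It does not. Their number and timing will be available; only the paired estimate is missing.
- *A reader might treat the SAP's omission of unscheduled visits from the model, or its n = 25 against the CIP's n = 5, as sources of bias.* Unscheduled scores fall at irregular times and fit poorly as a separate model variable, and the SAP's n is the larger. The SAP is also more specific than the CIP on covariates and the seed. CIP 13.1 lets lesser changes be described in the study report. These differences are housekeeping.
- *A reader might conclude that the primary p-value is unsafe.* Step 5 shows otherwise for an effect like that of the cited series. At 2 points, missing subjects would have to worsen on average.

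Some freedom in the model also has a reason: about 52 subjects may not support every covariate. A stated order of removal meets that need without putting the pain scores at risk.

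**Conclusion.** The point holds, as something that should be changed and not as a fatal flaw. With about a third of treated subjects planned to be missing, the analyses include none that allows missing subjects to fare worse than modelled or last seen. The SAP also weakens the CIP's commitment on the imputation variables.

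The main exposure is the size of the effect. A completers' mean at the 2-point clinically important difference would be -1.67 to -0.69 in all treated subjects for net gaps of 1 to 4 points. Significance against zero is at risk only when the true effect is near 2 points and the net gap is about 2.4 to 2.9.

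The text of the plan is clear on each element, so confidence in the gap itself is high. The magnitudes are illustrative: the net gap, correlations, dropout slope, normality and baseline mean are all assumed. Seventeen is a planning figure, and the procedure-date rule in SAP 7.9.1 may change the number imputed.

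**What to change.** 1. **Imputation model (SAP 7.9.1).** Turn the permissive wording into a requirement: the model will include worst pain at baseline, 3 days, 1 week, 1 month and 3 months, with age, Karnofsky score and time from diagnosis. If it does not converge, drop those three covariates first, in a stated order, before any pain score.
2. **Delta-adjusted MI on the treated set.** Add 0, 1, 2, 3 and 4 points to imputed 3-month scores, capped at 10. Report the mean, 95% CI and tipping delta by Rubin's rules, and the net shift achieved after the cap. Show results with deaths before month 3 imputed and with them left out.
3. **Keep** the completers' primary test and LOCF as planned.
4. **Housekeeping.** List the CIP-SAP differences in SAP 7.11.

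The cost is SAP wording and a little more programming, with no new data collection and no change to the sample size. The downside is that the treated-population estimate may look less favourable than the completers' result.

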### 7.5 Adjustments for Multiple Comparisons

At the time of the primary objective report, the primary objective will be tested at a two-sided alpha level of 0.05. There are no other hypothesis tests associated with the secondary objective or additional measures, so no adjustment for multiple endpoints is required.

### 7.6 Demographic and Other Baseline Characteristics

[figure not shown]
Demographic characteristics and baseline cancer and pain history will be summarized for all enrolled and treated subjects.

### 7.7 Treatment Characteristics

The RFA procedures will be summarized. The procedures will be summarized by overall procedure characteristics (procedure time, number of target sites, target site location(s), admission type, anesthesia methods, imaging guidance system) and also by individual procedure site characteristics (RFA approach, number of ablations within target site, technical success, cementoplasty performed and type, cement extravasation occurrence and clinical significance).

Revision 1.0

Page 10 of 15

Concomitant therapies will be summarized by the number of subjects taking each of the treatment types, and radiation treatment characteristics.

### 7.8 Interim Analyses

Regular reporting of study progress and safety experience will be made in annual progress reports.

The plan for the analyses of the primary objective and the other study objectives is described earlier in Section 5 Investigation Plan.

No formal statistical interim analyses of the study objectives are planned.

### 7.9 Evaluation of Objectives

The primary objective hypothesis will be tested after the sample size requirements for it have been met. The sample size requirement is 35 subjects successfully treated and completing the pain assessment at 3 months. Prior to the date the 35th subject completes the 3-month visit, the visit cut-off date will be estimated for the database snapshot. If additional subjects are enrolled later and also treated for metastatic lesions involving only the vertebral body, those additional subjects will be combined with the first group and summarized together in the Final Study Report. However, no additional hypothesis testing will be performed in the Final Study Report.

### 7.9.1 Primary Objective

To demonstrate an improvement from baseline to 3 months post radiofrequency ablation in worst pain score in the past 24 hours in subjects treated for metastatic lesions in only the thoracic and/or lumbar vertebral body(ies)

